### **3.3.4. Other Safety Endpoints**

Other safety endpoints include:

- Laboratory test
- Vital signs
- Electrocardiogram (ECG)
- Physical examination

## **4. ANALYSIS POPULATIONS AND ANALYSIS SETS**

### **4.1. Safety Population**

The Safety Population will include all FL and MZL subjects who received at least one dose of study drug. The safety population will be used for analyses of safety endpoints for the Final Analysis for the NDA submission.

## 4.2. Intent-to-Treat (ITT) Population

The ITT FL population will include all FL subjects randomized per Protocol Amendment 1 (two-arm design with randomization), and all enrolled FL subjects who received at least one dose of study drug per Protocol Amendment 2 or later amendment (single-arm, open-label design).

The ITT IS FL Population is defined as all FL subjects who are intended to receive ME-401 IS regimen, either per Protocol Amendment 1 or per Protocol Amendment 2 or later amendments, including subjects who:

- Were randomized to the ME-401 IS dosing regimen group (Group B) per Protocol Amendment 1
- Were randomized to the ME-401 CS dosing regimen group (Group A) per Protocol Amendment 1, but re-consented to Protocol Amendment 2 (for IS dosing regimen) prior to or on their Cycle 3 visit date
- Were enrolled per Protocol Amendment 2 or later amendment who received ME-401 IS dosing regimen.

The ITT CS Group in the ITT FL Population is defined as all FL subjects who are randomized to the ME-401 CS regimen group (Group A) per Protocol Amendment 1, and did not switch to IS dosing regimen at Cycle 3 visit per Protocol Amendment 2. More specifically, this population includes subjects who were originally randomized to the ME-401 CS dosing regimen group (Group A) per Protocol Amendment 1, had their Cycle 3 visits prior to when the subjects re-consented to Protocol Amendment 2, or discontinued treatment without being re-consented under Protocol Amendment 2.

The ITT MZL population is defined as all enrolled MZL subjects who received at least one dose of ME-401.

Subjects' original treatment assignments are documented in IVRS vendor's randomization listings.

- If the FL patients' ORIGINAL\_TREATMENT="ME-401 60 mg 1 wk on/3 wks off" or "Open Label Treatment", they will be included in ITT IS FL Population;
- If the FL patient's ORIGINAL\_TREATMENT="ME-401 60 mg daily", and
  - If VISIT\_TYPE="Cycle 3 Day 1" and VISIT\_DATE >= the date when subjects re-consented to Protocol Amendment 2 from Inform Consent CRF data from EDC, they will be included in ITT IS FL Population;
  - If VISIT\_TYPE="Cycle 3 Day 1" and VISIT\_DATE < the date when subjects re-consented to Protocol Amendment 2 from Inform Consent CRF data from EDC, the subject will be included in ITT CS Population;
  - If patients were never consented to Protocol Amendment 2, they will be included in ITT CS Population.

The ITT FL population and ITT MZL population will be used for the analyses of disposition, baseline characteristics, and efficacy endpoints. The overall ITT population (including both ITT FL and ITT MZL populations) will be used for the presentation of subjects in all subject listings.

To evaluate the impact of the covid-19 pandemic on ORR, a Modified ITT (mITT) Population is defined as all ITT FL or ITT MZL patients excluding who discontinued from treatment early due to covid-19 deaths with no post-baseline efficacy assessment.

### **4.3. Efficacy Analysis Populations and Analysis Sets**

The primary efficacy population in FL (PEP FL) is defined as the initial 91 consecutive subjects enrolled in the ITT IS FL Population.

The DOR Primary Analysis Set for FL will include subjects in the PEP FL who achieved PR or CR prior to first PD, that is reported before the data cutoff date for the FL Primary Analysis.

The DOR Supportive Analysis Set for FL will include subjects in the ITT IS FL who achieved PR or CR prior to first PD, that is reported before the data cutoff date for the NDA Analysis for FL.

The DOR Analysis Set for MZL will include subjects in the ITT MZL FL who achieved PR or CR prior to first PD, that is reported before the data cutoff date for the MZL Primary Analysis.

The efficacy evaluable (EE) population will include all subjects who received at least one dose of study drug and had at least one response assessment post baseline.

Subjects will be analyzed by randomized group per Protocol Amendment 1 and by enrolled group (IS dosing) per Protocol Amendments 2 and 3. EE population will be used for selected efficacy analyses.

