#### Sample Size for FL

The study will test the null hypothesis that the IRRC-reviewed ORR is  $\leq 48\%$  against the alternative hypothesis that it is  $\geq 65.5\%$ . The sample size for the PEP for FL is estimated to be 91 subjects, with at least 90% power and 1-sided alpha = 0.025. The selection of a null hypothesis of 48% was based on a review of the ORR reported with therapies that have full approval in the US for the treatment of relapsed FL (single agent rituximab, single agent bendamustine, lenalidomide plus rituximab, and obinutuzumab plus bendamustine) and therapies that have

accelerated approval in the US for the treatment of relapsed FL (tazemetostat [[Tazverik® US PI](#)], [duvelisib](#), [umbralisib \(Ukoniq™ US PI\)](#), [idelalisib](#), [copanlisib](#)), focusing on ORR reported in patients who have received  $\geq 2$  lines of therapy prior to enrollment. The selection of the alternative hypothesis of 65.5% was based on the results achieved with single agent zandelisib in Study ME-401-002, with an ORR of 70% observed in patients enrolled in the study after failure of  $\geq 2$  prior therapies (data on record).

Safety analysis will be performed based on the Safety Population, with analysis focused on the IS FL subjects at the primary analysis database lock for FL. With a total sample size of 120 FL subjects treated with ME-401 IS dosing regimen, if  $\leq 15$  subjects experience Grade  $\geq 3$  AESIs (i.e., subject incidence rate of  $\leq 12.5\%$  with 95% CI of 7.2–19.8%), the study can rule out the possibility of having a incidence rate  $\geq 20\%$  for Grade  $\geq 3$  AESIs with the IS dosing regimen. In addition, with a total sample size of 120 FL subjects, if  $\leq 5$  subjects experience a particular type of AE (i.e., subject incidence rate of  $\leq 4.2\%$  with 95% CI 1.4-9.5%), the study can rule out the possibility of having an incidence rate  $\geq 10\%$  for the AE.

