## 2.4. Determination of Sample Size

### Sample Size for FL

The study will test the null hypothesis that the IRRC-reviewed ORR is  $\leq 48\%$  against the alternative hypothesis that it is  $\geq 65.5\%$ . The sample size for the primary efficacy population for FL is estimated to be 91 subjects, with at least 90% power and 1-sided alpha = 0.025.

Safety analysis will be performed based on the Safety Population, with analysis focused on the IS FL subjects at the primary analysis database lock for FL submissions. With a total sample size of 120 FL subjects treated with ME-401 IS dosing regimen, if  $\leq 15$  subjects experience Grade  $\geq 3$  AESIs (i.e., subject incidence rate of  $\leq 12.5\%$  with 95% CI of 7.2–19.8%), the study can rule out the possibility of having an incidence rate  $\geq 20\%$  for Grade  $\geq 3$  AESIs with the IS dosing regimen. In addition, with a total sample size of 120 FL subjects, if  $\leq 5$  subjects experience a particular type of events (i.e., subject incidence rate of  $\leq 4.2\%$  with 95% CI 1.4–9.5%), the study can rule out the possibility of having an incidence rate of  $\geq 10\%$  for this AE.

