## 7. EFFICACY ANALYSIS

### 7.1. Primary Efficacy Endpoint and Analysis

The primary efficacy endpoint is ORR, defined as the proportion of subjects achieving the best response rating of CR or PR based on the Modified Lugano Classification, assessed by IRRC.

For Primary Analysis and NDA Analysis for FL, ORR will be evaluated by summarizing the number and percentage of subjects with the best overall response (CR/PR) prior to first PD as assessed by IRRC that is reported before the data cutoff date for the Primary Analysis, along with 2-sided 95% exact Clopper-Pearson confidence interval (CI). The primary efficacy analysis will be based on the Primary Efficacy Population for FL (PEP FL).

As a supportive analysis for NDA Analysis for FL, ORR will be analyzed

- using the ITT FL Population by including the PEP FL, ITT IS FL, ITT CS, ITT FL Total patients
- by summarizing the number (percentage) of patients who achieved PR or CR before the data cutoff date for the NDA Analysis for FL submission.

As sensitivity analyses, the above analyses in [Section 7.1](#) will be repeated for EE population and PP population.

All subjects who did not meet the criteria for an objective response by the analysis cut-off date will be considered non-responders.

To evaluate the impact of the covid-19 pandemic on efficacy of ME-401, the above analyses in [Section 7.1](#) will also be conducted using the Modified ITT Population in IS FL patients, i.e., patients who discontinued from treatment early due to covid-19 deaths with no post-baseline efficacy assessment will be excluded from the analysis.

Subgroup analysis of ORR (the proportion of subjects with the best overall response [CR/PR] prior to first PD as assessed by IRRC), that is reported before the data cutoff date for the Primary Analysis, will be performed by the subgroups defined in [Section 5.5](#), based on PEP FL and ITT MZL population. Forest plots will be provided for ORR and 95% CI in selected subgroups.

Waterfall plots of maximum percentage decrease in sum of the products of longest diameters (SPD) measured by the IRRC will be provided for the patients in the PEP FL and ITT MZL population.

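### The EE and PP sets class re-consented Group A subjects as CS and are not limited to the 91-subject PEP, so their ORR can differ from the primary ORR because the subjects differ

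*SAP*

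**What the plan says.** SAP 4.3 gives the primary efficacy population for FL as "defined as the initial 91 consecutive subjects enrolled in the ITT IS FL Population". SAP 4.2 builds ITT IS FL from three sources. One is subjects randomized to Group A (CS) under Protocol Amendment 1 "but re-consented to Protocol Amendment 2 (for IS dosing regimen) prior to or on their Cycle 3 visit date". Such a subject is IS by definition and can be one of the 91.

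SAP 4.3 defines EE as dosed subjects with at least one post-baseline response assessment. SAP 4.5 defines PP as dosed subjects with a response assessment and no major deviation. Neither definition mentions the PEP or limits itself to FL. Both carry the same grouping sentence: "Subjects will be analyzed by randomized group per Protocol Amendment 1 and by enrolled group (IS dosing) per Protocol Amendments 2 and 3".

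The COVID-modified set (mITT) in SAP 4.2 "is defined as all ITT FL or ITT MZL patients excluding who discontinued from treatment early due to covid-19 deaths" and who had no post-baseline efficacy assessment. It has no grouping sentence. SAP 7.1 says that its analyses are repeated for EE and PP as sensitivity analyses, and that they "will also be conducted using the Modified ITT Population in IS FL patients".

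SAP Table 4 plans ORR on PEP FL alone at the Primary Analysis. At the NDA Analysis it adds columns for ITT IS FL, ITT CS and ITT FL Total. It has no row for EE, PP or mITT.

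**The concern.** A sensitivity analysis is informative when it changes one thing. EE should show what happens when subjects without an assessment are dropped, PP when major deviators are dropped, and mITT when early COVID-19 deaths are dropped.

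As written, EE and PP can change up to three things at once: the factor of interest, the schedule label of re-consented Group A subjects, and the pool of subjects. If the EE or PP rate then differs from the primary rate, the report cannot say why. If it agrees, two shifts may have cancelled. The mITT analysis has a milder form of the problem: set beside the PEP result, it adds later IS FL subjects while it removes COVID-19 deaths.

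**Working it through.** **1. The plan's own figure.** The SAP gives the PEP size as "estimated to be 91 subjects, with at least 90% power and 1-sided alpha = 0.025". The protocol supplies the two rates: "The selection of a null hypothesis of 48% was based on a review of the ORR" and "The selection of the alternative hypothesis of 65.5% was based on the results achieved". Exact binomial test, n = 91: the smallest r with P(X ≥ r | 0.48) ≤ 0.025 is r = 54. Exact alpha is 0.0196 and power at 65.5% is 0.910. The Clopper-Pearson interval at 54/91 is 48.5% to 69.5%, so its lower bound clears 48%. The stated design reproduces. It depends on the PEP only, so nothing below touches it.

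**2. One subject, followed through the SAP.** Take a subject randomized to Group A who re-consented before the Cycle 3 visit.

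| SAP place | Set | Schedule group |
|---|---|---|
| 4.2 | ITT IS FL | IS |
| 4.3 | PEP FL, if among the first 91 | IS |
| 4.3 | EE | CS (randomized group) |
| 4.5 | PP | CS (randomized group) |
| 4.2 and 7.1 | mITT in IS FL patients | IS |

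The contradiction is confined to EE and PP.

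**3. Size of the relabelling.** Neither document gives the number of re-consented Group A subjects. Assume 60 responders among the 91 (65.9%, close to the alternative).
- One responder moved to CS: 59/90 = 65.6%, or -0.4 points.
- One non-responder moved: 60/90 = 66.7%, or +0.7 points.
- Five, ten or fifteen moved, responding at about the PEP rate: 57/86, 53/81 or 50/76, or +0.3, -0.5 or -0.1 points.
- Fifteen moved, extremes: all responders 45/76 = 59.2% (-6.7 points); none 60/76 = 78.9% (+13.0 points).

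**4. Size of the change of pool.** Protocol 8.3 reports 121 FL subjects treated on the IS, so 121 - 91 = 30 lie outside the PEP (29 with the SAP's planned 120). If those 30 differ from the PEP in ORR by δ points, the pooled rate moves by (30/121) × δ. For δ = 0, 5, 10 and 15 this is 0, 1.2, 2.5 and 3.7 points, in either direction. The range for δ is an assumption.

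If EE or PP were also pooled over histology, 32 MZL subjects at an assumed 46% to 80% ORR, added to an assumed 79/120 in IS FL, give (79 + 32 × 0.46)/152 = 61.7% to (79 + 32 × 0.80)/152 = 68.8%. That is -4.3 to +2.9 points from 65.9%.

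**5. Size of the effects being sought.** Within the PEP, dropping 2, 5 or 9 non-evaluable non-responders gives 60/89, 60/86 or 60/82, or +1.5, +3.8 or +7.2 points. Dropping 1, 2 or 4 COVID-19 deaths gives 60/90, 60/89 or 60/87, or +0.7, +1.5 or +3.0 points. The shifts in steps 3 and 4 can be as large as these.

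**6. The mITT comparator.** At the NDA Analysis, mITT in IS FL can be set beside the ITT IS FL column. With an assumed 79/120, dropping 1, 2 or 4 COVID-19 deaths gives 79/119, 79/118 or 79/116, or +0.6, +1.1 or +2.3 points. The two sets differ only in the excluded deaths, so that comparison is clean.

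**The case against.** The best defence is that SAP 7.1 repeats analyses already laid out by population. It can be read as the PEP FL, ITT IS FL, ITT CS and ITT FL columns, each restricted to evaluable or per-protocol subjects. EE and PP would then be nested in the PEP. That reading is possible, so nesting is unstated and not excluded. But the SAP nests explicitly where it means to: the DOR Primary Analysis Set is limited to PEP subjects. Intersection also leaves the grouping sentence in force, and that sentence still labels some PEP members CS.

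Several further points stand. The shifts may be close to nil: at 65.5% ORR in the later subjects the pooled rate moves by about -0.1 points. Shorter follow-up is a weak reason to expect a lower ORR, because protocol 1.6.2.4 reports that 48 of 54 Phase 1b responses (89%) were seen at the assessment after two cycles. The grouping sentence stops at Amendment 3, but enrolment since Amendment 2 has been to IS only, so this is dated wording without a shown consequence. MZL was not part of the Group A/B conflict, so the MZL sensitivity analysis in EE does not inherit it.

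A reader might infer that all three sets class re-consented subjects as CS, or that the COVID analysis can never isolate COVID. The documents do not support either. The mITT set has no grouping rule and is run in IS FL, and the NDA Analysis supplies its comparator.

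**Conclusion.** The point holds for EE and PP. Their grouping rule contradicts SAP 4.2, and their definitions state no restriction to the PEP, so a difference from the primary ORR can come from different subjects. For mITT it holds only against the PEP, chiefly at the Primary Analysis, where Table 4 plans no other ORR population; up to about 30 later IS FL subjects would enter there.

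The size cannot be fixed from the documents. It depends on the unstated number of re-consented subjects and on how they and the later subjects respond. On the assumptions above it is -0.4 or +0.7 points per subject moved and 0 to 3.7 points for the later subjects. It would be wrong to count each moved subject as 1/91 = 1.1 points: that is a share of the denominator, and the subject leaves numerator and denominator together.

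A reader might also infer that the primary result is in doubt. It is not: the test, its alpha and its power rest on the PEP alone. What is weakened is the support that the EE and PP analyses can lend to it.

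**What to change.** - In SAP 4.3 and 4.5, replace the sentence on analysis by randomized group with the IS/CS assignment of SAP 4.2, worded for Amendment 2 and later. The protocol's EE definition (11.2.1) has no such sentence, so no conflict arises.
- In SAP 7.1, state that the EE, PP and mITT analyses of ORR are run within PEP FL for the primary analysis, within ITT IS FL for the supportive analysis (which keeps the existing mITT analysis in IS FL), and within ITT MZL separately.
- Reconcile SAP 4.5, which assigns PP to the primary efficacy analyses, with SAP 7.1, which makes it a sensitivity analysis.

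The cost is SAP wording and population flags. No new data, subjects or tests are needed.

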### **4.4. Pharmacokinetic (PK) Population**

The PK population will include all subjects who received at least one dose of ME-401 and who had evaluable PK data, i.e. quantifiable ME-401 concentrations. The PK population will be used for the analyses of PK endpoints. PK Analysis will be performed separately by central Lab (LGC).

### **4.5. Per Protocol (PP) Population**

The per protocol population will include all subjects who received at least one dose of study drug, had at least one response assessment after Day 1, and did not have any major protocol deviation during the study. Subjects will be analyzed by randomized group per Protocol Amendment 1 and by enrolled group (IS dosing) per Protocol Amendments 2 and 3. PP population will be used for primary efficacy analyses.

### **4.6. Protocol Deviations**

Study protocol deviations will be identified by the clinical team and assigned within the appropriate deviation category. All protocol deviations will be collected separately from the database, and graded as minor or major before the database lock. A summary table for number

and percentage of subjects with major protocol will be summarized by type of deviation and treatment group. A listing will be generated for protocol deviations.

## 5. GENERAL ASPECTS FOR STATISTICAL ANALYSIS

### 5.1. General Methods

- All statistical analyses and summaries will be performed using SAS® 9.4 or higher.
- Unless otherwise specified, safety summarized will be presented for all dosed patients by actual dose schedule (CS and IS). For IS group, the safety tables further have 3 sub-columns: FL, MZL, and all IS.
- Detailed types of analyses and corresponding populations for planned Primary Analysis and NDA Analysis for FL is shown in [Table 4](#).
- Unless otherwise specified, descriptive statistics for continuous data will include the number of subjects (n), mean, standard deviation (SD), minimum and maximum. For discrete variables, frequency count and percentages will be computed. Percentages based on frequency counts will be based on available data, and denominators will generally exclude missing values, unless otherwise stated. All percentages will be presented with one decimal, unless otherwise specified. Percentages equal to 100 will be presented as 100, and percentages will not be presented for zero frequencies.
- The same number of decimal places as in the raw data will be presented when reporting min and max, 1 more decimal place than in the raw data will be presented when reporting mean and median, and 2 more decimal places than in the raw data will be presented when reporting SD. If the raw data has 3 decimal places or more, 3 decimal places will be presented for mean, median, Q1/Q3, and SD. For continuous variables assessed at baseline and post-baseline, the change from baseline summary statistics will also be presented.
- Subject listings of all data in the database will be provided, including data collected in the electronic case report form (eCRF) as well as data transferred electronically. Measurements from subjects excluded from the pre-defined analysis populations or extra measurements (such as unscheduled or repeat assessments) will not be included in summary tables unless specified otherwise, but will be included in the subject listings. Listings will be sorted by treatment groups, subject number, and visit/collection date/time if applicable, unless otherwise stated.
- All fractional numeric values will be presented with a zero to the left of the decimal point (for example, 0.12 - 0.30, not .12 - .30).

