**Table 4: ME-401 Toxicity Management (Continued)**

Toxicity	Grade*	Management of ME-401	Management of Toxicity
Cutaneous Reactions and Mucositis	2	
 
Hold ME-401 unless rash ascertained to be unrelated to study drug.
 
If ME-401 is held, once AE resolves to Grade <math>\leq 1</math>, resume ME-401 at 60 mg administered on the IS.
 
	
 
Monitor subjects and determine cause of rash.
 
Per Investigator's discretion, antihistamines, topical steroids, and systemic steroids may be given.
 

	<math>\geq 3</math>	
 
Hold ME-401 until AE resolves to Grade <math>\leq 1</math>, then, if clinically indicated, resume ME-401 at 60 mg administered on the IS.
 
For recurrence of Grade 3, permanently discontinue ME-401.
 
	
 
Monitor subjects as clinically indicated until resolution.
 
Oral antihistamines and systemic corticosteroids such as prednisone 0.5–1 mg/kg/day (or equivalent dose of methylprednisolone) should be given until rash resolves to Grade <math>\leq 1</math>.
 

	Any	
 
Permanently discontinue ME-401 for life-threatening toxicity, Stevens-Johnson syndrome of any grade, and TENS of any grade.
 
	
 
Treat per institutional standard of care.
 

Hepatotoxicity	2	
 
For ALT/AST <math>>3-5 \times</math> ULN but <math><5 \times</math> ULN, maintain ME-401 treatment dose and schedule.
 
	
 
Monitor ALT/AST weekly until resolved to Grade <math>\leq 1</math> or baseline level.
 

	3	
 
For ALT/AST <math>>5-20 \times</math> ULN, hold ME-401.
 
Resume ME-401 at 60 mg administered on the IS.
 
For recurrence of Grade 3, permanently discontinue ME-401.
 
	
 
Monitor ALT/AST once a week until resolved to Grade <math>\leq 1</math> or baseline level.
 
Treat per institutional standard of care, which may include a course of corticosteroids if clinically indicated.
 
Assess if Hy's law applies.
 

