## 5.4. Monitoring and Prophylaxis of Opportunistic Infection

### 5.4.1. Monitoring for Opportunistic Infection

In addition to the clinical review and laboratory tests outlined in the Schedule of Assessments ([Appendix 1](#)), the following should be performed in all subjects prior to start of every cycle of treatment with ME-401:

- Evaluation of any new onset or worsening of pulmonary symptoms (i.e., cough, dyspnea, or fever) that includes a lung examination at each visit prior to treatment to rule out opportunistic infection (OI), including PJP *Pneumocystis jirovecii* pneumonia/PCP (*pneumocystis* pneumonia).
- Laboratory tests:
  - CD4 (for subjects with signs of infection)
  - Blood cultures if febrile neutropenia occurs, or when ANC by NCI CTCAE is Grade 4
  - PCR for CMV (every cycle for first 6 months of treatment and every 3 months thereafter). If PCR test is positive for CMV and treatment is initiated, then treatment with ME-401 should be delayed until recovery. Treatment of CMV should be initiated based on local SOC. Retreatment with ME-401 will be allowed on the IS once PCR test for CMV is negative. Please note: quantitative results from PCR measurements must be reported for all CMV assessments.

Implement enhanced monitoring prior to start of every cycle of treatment with ME-401 when prior medical history or laboratory parameters could be associated with one of the following risk factors:

- Intensive chemotherapy ( $\geq 2$  lines of myelosuppressive cytotoxic therapy)

- History of symptomatic CMV infection, systemic herpes
- History of lower respiratory tract infection
- History of immunodeficiency in the last 12 months (excluding lymphoma)
- Lymphocyte count  $<500/\text{mm}^3$  while on treatment in clinical study

For subjects with identified risk factors and those who developed an OI while on study treatment, additional assessments may include:

- CD4 and CD8 count and ratio, c-reactive protein, blood cultures
- Any additional laboratory and diagnostic methods according to local SOC reported as unscheduled laboratory and diagnostic methods of assessment
- Radiological imaging (i.e., chest X-ray or CT scans)
  - Note: Treatment of the OI that started while on study should be based on local SOC.

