### **5.4. Visit Windows**

For study assessment days, there is  $\pm 3$ -day window allowable for each clinic visit during Cycle 1. For Cycles 2 through 25, the allowable window is  $\pm 7$  days. After Cycle 25, the allowable window is  $\pm 1$  month for each clinic visit and its associated assessments.

There is no plan to re-assign visits based on actual visit dates. The analysis will be based nominal visit/time points collected.

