#### **8.4. Laboratory Evaluations**

Lab evaluations will include hematology (including coagulation), serum chemistry, urinalysis, pregnancy test, HIV testing, Hepatitis B and Hepatitis C testing, bone marrow aspiration/biopsy, PCR tests for CMV and opportunistic infection (OI) monitoring.

For statistical and graphical summaries of the laboratory tests, values below or above the limit of detection (e.g., '< 3' or '>500') are substituted with the lower limit of detection minus 1% for values below the lower limit and are substituted with the upper limit of detection plus 1% for values above the upper limit (e.g., '< 3' is substituted by '2.97', '> 500' is substituted by '505'). In data listings, the values are shown including the < or > sign.

Results from the hematology, chemistry, and urinalysis will be summarized by visit using descriptive statistics, including the observed values and change from baseline values for numeric parameters and distribution of categories for categorical parameters. Boxplots by visit will be generated for selected hematology/chemistry parameters.

In addition, the incidence rate of grade 3 and above toxicity for selected hematology and chemistry parameters will be summarized by visit. Separate listings will be produced for subjects with grade 3 and above toxicity for selected hematology and chemistry parameters.

Treatment-emergent toxicities are defined as the worsening of lab toxicity grade comparing to the baseline. The incidence rate of treatment-emergent grade 3 and above toxicity for hematology and chemistry parameters will be summarized by visit.

By-subject listings of hematology, serum chemistry, and urinalysis tests, including lab normal ranges, will be provided. Derived CTCAE grades will be included in listings, as applicable.

The following lab data will be listed only: pregnancy test, HIV, Hepatitis B and Hepatitis C tests, bone marrow aspiration/biopsy, CMV titers, and OI monitoring.

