#### **8.6. Cardiac Evaluations**

12-lead ECGs parameters including hear rate, RR interval, PR interval, QRS interval and QTcF will be assessed. For each parameter, the observed values and change from baseline will be summarized by visit.

The overall ECGs interpretations will be collected as ‘Normal’, ‘Abnormal, not clinically significant’ and ‘Abnormal, clinically significant. Shift tables from baseline will be produced based on these categories for each post-baseline. In addition, the incidence rate of grade 3 and above QT prolongation will be summarized by visit.

All 12-lead ECG data will be listed. In addition, the results of echocardiogram will be listed.

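### Grade ≥3 laboratory and QT tables are by nominal visit and leave out unscheduled values, so they miss measured peaks and never give the proportion of subjects ever affected

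*SAP*

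**What the plan says.** SAP 5.1 (General Methods) sets a default for all measurements: "extra measurements (such as unscheduled or repeat assessments) will not be included in summary tables unless specified otherwise". Such values are kept only in listings. SAP 5.4 adds that "There is no plan to re-assign visits based on actual visit dates" and that "The analysis will be based nominal visit/time points collected".

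SAP 8.4 plans two tables of Grade ≥3 laboratory toxicity. One covers selected hematology and chemistry parameters. For the other, "The incidence rate of treatment-emergent grade 3 and above toxicity for hematology and chemistry parameters will be summarized by visit". SAP 8.6 does the same for ECG: "the incidence rate of grade 3 and above QT prolongation will be summarized by visit". Neither section uses the opening that SAP 5.1 leaves for a specified exception, and neither defines a worst post-baseline grade. The ECG shift tables are by visit and use the overall interpretation, not QTcF.

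Protocol Table 4 (toxicity management) orders tests that fall between visits. Its instruction from Grade 2 hepatotoxicity begins "Monitor ALT/AST weekly until resolved to Grade", with recovery to Grade 1 or the baseline value as the end point. Blood counts are weekly once Grade 3 hematological toxicity is reached, and platelets are checked every 3 days in one Grade 4 row. Protocol 9.6 allows ECGs as clinically indicated. Protocol 11.2.2 lists treatment-emergent abnormal laboratory changes among the planned safety summaries.

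**The concern.** There are two separate defects.

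First, an off-schedule value of Grade 3 or worse is measured and stored, but no laboratory or ECG table counts it. It appears only in subject listings.

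Second, a set of by-visit rates does not give the proportion of subjects ever affected. With a common denominator, the number ever affected lies anywhere between the largest single-visit count and the sum of the counts over visits. This would hold even if unscheduled values were included.

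In an open-label single-arm study, objectively graded laboratory values are a check on investigator-reported AEs. The protocol's rationale for the intermittent schedule (section 2.3) is fewer delayed toxicities, transaminase increases among them. A laboratory table that omits measured peaks weakens that check.

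**Working it through.** **1. The plan's own safety figure.** SAP 2.4 gives 7.2–19.8% as the 95% CI for 15 of 120 subjects with Grade ≥3 AESIs. The exact Clopper-Pearson limits are BetaInv(0.025; x, n−x+1) and BetaInv(0.975; x+1, n−x). With x = 15 and n = 120 they give 7.2–19.8%, which reproduces the plan. With x = 16 they give 7.8–20.7%, so one more subject would cross 20%. This calculation counts reported AESIs, not by-visit laboratory values, so the SAP 5.1 rule does not alter it.

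**2. How far apart the counted values are.** CBC and chemistry draws (protocol Appendix 1) fall on Days 1, 8, 15, 29, 43, 57, 85, 113, 141, 169, 253, 337 and so on. The gaps are 7, 7, 14, 14, 14, 28 (four times), then 84 days. After Cycle 6 the scheduled ECGs on treatment are at Cycles 13, 19 and 25: gaps of 7×28 = 196, 6×28 = 168 and 168 days.

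**3. How coarse that schedule is.** If an episode lasts d days and starts at random within a gap of g days, the chance that it covers a scheduled draw is min(1, d/g). The documents give no durations, so d is an assumption.

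| Assumed d (days) | g = 14 | g = 28 | g = 84 |
|---|---|---|---|
| 7 | 50% | 25% | 8% |
| 14 | 100% | 50% | 17% |
| 21 | 100% | 75% | 25% |
| 28 | 100% | 100% | 33% |

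This describes the schedule only. It does not measure the understatement (see verdict).

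**4. Following cases through the plan.**

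- *ALT Grade 2 at the Cycle 7 visit, Grade 3 at a weekly repeat, recovered by Cycle 10.* Laboratory tables: not counted as Grade ≥3. AE tables: protocol Table 4 calls for a hold at Grade 3, a deterioration that changes treatment is an AE under protocol 6.1, and AST/ALT from Grade 2 is an AESI under protocol 5.3.2. SAP 8.3.3 counts the subject among Grade ≥3 AESIs and in TEAEs by maximum grade.
- *Grade 3 neutropenia at a scheduled draw, Grade 4 at a weekly repeat.* Laboratory tables: already counted as Grade ≥3 at the scheduled visit; only the rise to Grade 4 is lost.
- *Grade 3 neutropenia or thrombocytopenia first seen on an off-schedule count, no symptoms, dosing continued as protocol Table 4 permits, not judged clinically significant.* Laboratory tables: not counted. AE tables: not an AE under protocol 6.1, so not counted. It is found only in listings.
- *Grade 3 QT prolongation on an ECG done as clinically indicated.* QT table: not counted. AE tables: counted only if it meets protocol 6.1.

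**The case against.** The strongest reply is that the tables carrying the safety message are not visit-based. TEAEs and cytopenia events are tabulated by maximum grade, Grade ≥3 AESIs by type and preferred term, and SAP 8.3 counts each subject once at the worst grade. SAP 8.3.4 also analyses time to first Grade ≥3 AESI. The protocol's case for the intermittent schedule and the sample-size rule-out both rest on AE and AESI counts. All of this stands. A reader might infer that the rule understates toxicity incidence in general, or the AESI rate; the documents do not support that.

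Three further limits stand:

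- CBC and chemistry are drawn at every clinic visit except the Day 7 PK visits, and the repeat tests in protocol Table 4 follow a toxicity already found.
- Protocol Table 4 orders no repeat ECGs, so the QT part rests only on ECGs done as clinically indicated.
- Opportunistic-infection tests are listed only under SAP 8.4. Although the protocol has some of them "reported as unscheduled laboratory and diagnostic methods of assessment", there is no incidence table for the rule to distort.

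Listings do keep the values, and SAP 8.4 gives Grade ≥3 values of selected parameters their own listing. But a listing gives no count, and the third case in the working is counted nowhere.

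**Conclusion.** The point holds for the laboratory and ECG tables. As written, they omit Grade ≥3 values measured between scheduled visits and do not report how many subjects were ever affected. The direction is known: adding measured values can only raise or leave unchanged a count of subjects with Grade ≥3. The AE tables recover most transaminase peaks that repeat testing would find. They do not recover a Grade ≥3 value that is silent, changes no treatment and is not judged clinically significant.

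The size cannot be computed, because the documents give neither episode durations nor laboratory event rates. A reader might take 1 − 28/84 = 67% to 1 − 14/84 = 83% as the share of peaks missing after Cycle 7. That does not follow. Repeat tests are triggered by an earlier abnormal value, so episodes found that way do not start at random between visits. An episode with no trigger is never measured, and no table could recover it.

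The conclusion assumes that SAP 5.1 is applied as written and that the repeat tests are stored as unscheduled rather than under a nominal visit.

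**What to change.** In SAP 8.4 and 8.6, as a stated exception to SAP 5.1:

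- For each parameter, give the number and percentage of subjects whose worst post-baseline CTCAE grade is 3 or higher, over all scheduled and unscheduled values in the treatment-emergent window (first dose to 30 days after last dose).
- Add shift tables from baseline grade to worst grade; for ECG, from baseline to worst QTcF category.
- Keep the by-visit tables and boxplots on nominal visits, labelled as descriptive.

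The cost is a few lines of SAP text and a few standard tables, with no new data collection. The only downside is that the reported laboratory toxicity rate may look less favourable.
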